**7.3. Study drugs background****7.3.1. Idelalisib**

Idelalisib is indicated in combination with rituximab, ofatumumab or bendamustine with rituximab for the treatment of patients with chronic lymphocytic leukemia who have received at least one prior therapy and for the treatment of patients with refractory indolent non-Hodgkin lymphoma (iNHL). Idelalisib should be used only in patients with limited treatment options. Idelalisib is a potent competitive inhibitor of the ATP binding site of the PI3K p110 $\delta$  catalytic domain, which has been shown to be prominently expressed in cells of hematopoietic origin [18, 19]. Inhibition of

PI3K $\delta$  has been shown to modulate cellular functions including motility, proliferation, survival, and recruitment of additional intracellular signaling enzymes through the B-cell receptor (BCR). B-cell receptor signaling is a central pathologic mechanism in B-cell malignancies in that it promotes leukemia and lymphoma cell survival and proliferation; disruption of BCR signaling can be lethal to malignant B cells. The effects of p110 $\delta$  on lymphocyte activation/function, cellular proliferation, and protection from apoptosis provide the rationale for targeting this isoform as a therapy for hematologic malignancies.

Idelalisib is an orally bioavailable, new chemical entity with a molecular weight of approximately 415 daltons. Its chemical name is 5-fluoro-3-phenyl-2-[(1S)-1-(9H-purin-6-ylamino)propyl]quinazolin-4(3H)-one). Idelalisib is a chiral compound with a single chiral center at C3. The compound is a single enantiomer with the (S) configuration.

Idelalisib is a new valid option for relapsed FL. In a phase 2 study of 125 patients with indolent NHL who were refractory to both rituximab and an alkylating agent, idelalisib was administered at a dose of 150 mg twice daily until PD or patient withdrawal [6]. The response rate was 57% with a median duration of 12.5 months. Response rates and duration in the FL subset were similar to the overall population. Grade 3 or higher toxicities included neutropenia (27%), transaminase elevations (13%), diarrhea (13%), and pneumonia (7%). Based upon this data, idelalisib received accelerated approval by the FDA in 2014. Efficacy results were confirmed even in a real life context [20].

Idelalisib in combination with rituximab, bendamustine and or rituximab+bendamustine is also being evaluated in subjects with relapsed/refractory iNHL with an ORR >75% in all the four cohorts (phase I study) [21]. Due to safety signal observed in idelalisib combination front-line CLL and early-line relapsed iNHL studies have been terminated as the risk/benefit profile was deemed unlikely to be favorable. Following completion of the CHMP (Committee of Human Medicinal Products) review, the benefit-risk balance of idelalisib in combination with rituximab for the treatment of relapsed CLL, including patients with 17p deletion or TP53 mutation, and idelalisib monotherapy for the treatment of refractory FL remains positive. CHMP concluded that the risk of serious infection is relevant to all indications. Risk minimization measures for serious infections have been implemented, in particular for *Pneumocystis jirovecii* pneumonia (PJP) and cytomegalovirus (CMV) infection. For further details please consult the last drug Investigator Brochure (IB).

### 7.3.2. Obinutuzumab

Obinutuzumab (also known as RO5072759, GA101, GAZYVA®, GAZYVARO™) is a humanized glycoengineered type II anti-CD20 monoclonal antibody (moAb). Obinutuzumab was derived by humanization of the parental B-Ly1 mouse antibody and subsequent glycoengineering leading to the following characteristics: high-affinity binding to the CD20 antigen, high antibody-dependent cellular cytotoxicity (ADCC), and antibody-dependent cellular phagocytosis (ADCP); low complement-dependent cytotoxicity (CDC) activity; and high direct cell death induction. As of July 2016, obinutuzumab in combination with bendamustine received regulatory approval for the treatment of patients with relapsed/ refractory FL in multiple countries including the US, Switzerland, and the EU.

Obinutuzumab drug substance is manufactured by fermentation of a recombinant mammalian cell line and subsequent purification of the antibody. An antibody-producing cell line was established from a Chinese hamster ovary (CHO) K1 cell line.

In the monotherapy setting (studies BO20999, BO21003, YP25623, and JO21900), the proportion of patients who had a response (CR or PR) at the end of treatment ranged from 28% (11/40 patients) to 58% (7/12 patients). Although these patients had treatment-refractory or relapsed disease and been treated with several prior therapies, some patients in studies BO20999, BO21003 Phase II, and JO21900 achieved a CR by the end-of-treatment assessment. In addition, in study YP25623 one DLBCL patient achieved a CRu and 2 patients achieved a PR. Six of the 13 patients with FL (46%) had a PR; no patient with NHL (DLBCL and FL) achieved a CR.

In the chemotherapy combination studies BO21000 and GAO4915g the proportion of patients achieving a response (CR or PR) was 82% among previously untreated DLBCL patients using Cheson 2007 criteria [22] and exceeded 90% among patients with previously untreated or relapsed/refractory FL. The CR rate was also higher than in the monotherapy studies (35-39% in previously untreated FL, 39-50% in relapsed/refractory FL and 55% in previously untreated DLBCL).

At a pre-planned interim analysis, the pivotal study GAO4753g met its primary objective of showing a difference in IRC-assessed PFS between treatment arms. Treatment with G-bendamustine resulted in a clinically meaningful and statistically significant reduction by 45% in the risk of IRC-assessed PFS (progression or death) compared with bendamustine alone (stratified analysis: HR 0.55, 95% CI [0.40, 0.74]; log-rank p-value  $\leq$  0.0001).

Furthermore, on 20 May 2016 a pre-planned interim analysis of the pivotal study BO21223 was performed, and the IDMC recommended to unblind and fully analyze the study. The results showed that obinutuzumab-based treatment significantly reduced the risk of disease progression or death (PFS, as assessed by investigator) compared to rituximab-based treatment in patients with previously untreated advanced FL. No new safety signals were detected. EMA has approved obinutuzumab in combination with bendamustine chemotherapy followed by obinutuzumab maintenance in people with FL who did not respond or who progressed during or up to six months after treatment with rituximab or a rituximab-containing regimen.

The approval is based on results from the pivotal phase III GADOLIN study [5, 23] which showed that obinutuzumab plus bendamustine, followed by obinutuzumab alone resulted in a 52 percent reduction (HR=0.48, 95 percent CI 0.34-0.68,  $p < 0.0001$ ) in the risk of disease worsening or death (PFS), compared to bendamustine alone, as evaluated by an independent review committee. As assessed by investigator review, median PFS with the obinutuzumab regimen was more than double that with bendamustine alone (29.2 months vs. 13.7 months; HR=0.48, 95 percent CI 0.35-0.67,  $p < 0.0001$ ). People who received the obinutuzumab regimen also showed a 38 percent reduction (HR=0.62, 95 percent CI 0.39-0.98) in the risk of death (OS) compared to those who received bendamustine alone. For further details please consult the last drug IB.

Obinutuzumab has also been investigated in the frontline setting. The GALLIUM study (clinicaltrials.gov identifier NCT01332968) is an international randomized phase 3 study comparing obinutuzumab plus chemotherapy (with obinutuzumab maintenance) to rituximab plus chemotherapy (with rituximab maintenance) in previously untreated advanced-stage FL. A total of 1202 patients with follicular lymphoma were randomized in the GALLIUM trial (601 patients in each group) [24]. After a median follow-up of 34.5 months, a planned interim analysis showed that obinutuzumab-based chemotherapy resulted in a significantly lower risk of progression, relapse, or death than rituximab-based chemotherapy (estimated 3-year PFS rate of 80.0% and 73.3%, respectively;  $P = 0.001$ ). No difference emerged between the two groups with respect to other time-to-event endpoints. No significant difference was observed in the rate of response according to CT-based assessment as well. Grade 3-5 adverse events and SAEs were more frequent with obinutuzumab than with rituximab (74.6% vs. 67.8% and 46.1% vs. 39.9%, respectively), but the rates of toxic deaths were similar in the two groups (4.0% and 3.4%, respectively). The most common adverse events were infusion-related events that were considered by the investigators to be largely due to obinutuzumab in 353 of 595 patients and to rituximab in 292 of 597 patients (59.3% and 48.9%, respectively;  $P < 0.001$ ). In conclusion, the GALLIUM trial showed that the replacement of rituximab with obinutuzumab in the context of immunochemotherapy and maintenance therapy in first line resulted in significantly longer PFS, but at the expenses of an higher frequency of high-grade adverse events [24].

## 8. STUDY RATIONALE

The new frontier in the treatment of FL is the development of non-cytotoxic combination therapies, able to offer to patients a “chemo-free” approach, with the same efficacy of conventional

chemotherapy but less toxicity. The paradigm of this approach is currently represented by the R-square regimen (rituximab + lenalidomide) which has shown an ORR of 77% with a CR rate of 41% [25] in relapsed/refractory FL and is currently under investigation in the frontline setting.

The combination of idelalisib with obinutuzumab would address a persistent unmet medical need with the same non-chemo approach: the design and conduct of this study is supported by knowledge of the natural history and current therapies for the disease, and the information regarding idelalisib and obinutuzumab mechanism of action and safety profile.

Idelalisib is a potent and highly selective, small-molecule, oral inhibitor of the delta isoform of the phosphatidylinositol-3 kinase (PI3K $\delta$ ), being able to block the PI3K $\delta$ -AKT signaling and promoting apoptosis, as shown in vitro in lymphoid cell lines and in vivo. Idelalisib has shown an ORR of 56% in heavily pretreated FL patients refractory to both rituximab and alkylating agents, with a CR rate of 14% and a median PFS of 11 months [6]. The potential for clinical efficacy of idelalisib in combination with an anti-CD20 monoclonal antibody in patients with relapsed or refractory indolent non-Hodgkin lymphomas (in particular in FL) is supported by the observed antitumor activity of idelalisib given in combination with rituximab in a phase I study with an ORR of 75% and a CR rate of 22% [21].

Obinutuzumab is a type II glycoengineered humanized anti-CD20 monoclonal antibody. Compared to rituximab, it shows an increased direct cell death induction and antibody-dependent cytotoxicity due to the glycoengineering, with also a superior B-cell depletion effect. It has shown its efficacy as single agent in heavily pretreated relapsed/refractory FL patients with a ORR of 55% and a CR of 9%, being well tolerated and with no dose limiting toxicities [26]. Moreover, it has been also safely and effectively combined with CHOP and FC chemotherapy regimens in the GAUDI study [27], showing remarkable ORR (96% and 93% respectively).

### ***Benefit/Risk balance of the combination idelalisib + obinutuzumab***

The association of idelalisib and obinutuzumab is a "chemo-free" therapy with potential good therapeutic efficacy counterbalanced by an acceptable toxicity profile. In particular, the reduced duration of idelalisib administration planned by the study significantly decreases the risk for toxicity previously reported with longer therapy, even if it still maintains the same therapeutic efficacy. Furthermore, idelalisib has a completely different mechanism of action with respect the classic chemotherapy, as well as the addition advantage of the oral administration.

## **9. STUDY OBJECTIVES**

### **9.1. Primary Objective**

- To evaluate the efficacy in terms of clinical response in patients treated with the combination of obinutuzumab and idelalisib.

### **9.2. Secondary Objective**

- To assess efficacy in terms of progression-free survival and overall survival
- To assess the safety and the feasibility of the combination of obinutuzumab and idelalisib.

### **9.3. Primary Endpoint**

**Overall response rate (ORR):** ORR will be assessed by investigator after the 6th cycle (end of induction phase) of therapy with the combination of obinutuzumab and idelalisib as defined by 2014 Lugano criteria [28]. Last available clinical response will be considered for patients who will permanently discontinue both drugs of the experimental combination before the completion of the 6th cycle (planned duration of induction phase) for any cause. Patients who will have no tumor assessment after the start of therapy will be considered non-responsive.

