#### 4. SYNOPSIS

Study ID	FIL_GAUDEALIS
Eudract N°	2018-001229-18
Title of the study	Idelalisib Plus Obinutuzumab In Patients With Relapsed/Refractory Follicular Lymphoma: A Phase 2, Single-Arm, Multicentric Study.
Phase of the study	Phase II single arm study
Investigational product	Obinutuzumab Idelalisib
Protocol version	Version 2.0 of May 29, 2019
Centers	12 sites within FIL (Fondazione Italiana Linfomi) centres. Coordinating Center: Institute of Hematology, AOU Policlinico S.Orsola-Malpighi, University of Bologna
Study Objectives and Endpoints	
Primary Objective To evaluate the efficacy in terms of clinical response in patients treated with combination therapy of idelalisib and obinutuzumab
 
Secondary Objectives
 
 
• To assess efficacy in terms of progression-free survival (PFS) and overall survival (OS).
 
• To assess the safety of the combination therapy and patients' compliance to treatment;
 
 
Primary Endpoint Investigator's assessed Overall response rate (ORR) at the end of induction phase of patients treated with a chemo-free combination with obinutuzumab and idelalisib. Overall response rate (ORR) is defined as the proportion of patients with at least a partial response (PR), as defined by 2014 Lugano criteria.
 
Secondary Endpoints
 
 
- Overall survival (OS) rate;
 
- Progression-free survival (PFS) rate;
 
- patients' withdrawal rate, incidence and nature of any severe adverse events, hospitalization rate throughout the study, and patients' compliance to oral treatment, incidence of any adverse events occurring during and right after treatment
 

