### **15.8. Early withdrawn (EW)**

discontinuation from study treatment

- Physical Examination;
- ECOG;
- Vital Signs;
- Hematology including Hemoglobin, Platelets, White blood cell count (WBC) with differential;
- Blood chemistry including creatinine, total bilirubin, LDH, AST, ALT, serum proteins with electrophoresis, immunoglobulin levels;
- Pregnancy test (if applicable);
- Electrocardiograms;
- LVEF by either bi-dimensional echocardiogram or cardiac scintigraphy (MUGA);
- Measurable lesion assessment on CT scan of neck, chest, abdomen and pelvis, to be performed with and without contrast unless the subject already has had per-protocol scan  $\leq 4$  weeks prior;
- FDG-PET scan (mandatory) unless the subject already has had per-protocol scan  $\leq 4$  weeks prior;
- Drug accountability
- AEs assessment
- Recording of concomitant medications.

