## **17. STATISTICAL CONSIDERATIONS**

### **17.1. Sample size**

Optimal Simon's two-stage design [32] has been used to calculate the sample size.

The null hypothesis that the true response rate is 55% (response rate of idelalisib single agent) [6] will be tested against a one-sided alternative response rate of 75% (response of obinutuzumab in combination) [23]. Last available clinical response will be considered for patients who will permanently discontinue for any cause both drugs of the experimental combination before the completion of the 6th cycle (planned duration of induction phase).

For the first stage, the accrual will be suspended when 15 patients will have started experimental therapy. If there are 9 or fewer responses in these 15 patients, the study will be stopped.

Otherwise, enrollment will be reopened until 28 additional patients will start experimental therapy for a total of 43. The null hypothesis will be rejected if 29 or more responses are observed in 43 patients.

This design yields a type I error rate of 5% and power of 80% when the true response rate is 75%.

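### Patients who die or start new anti-lymphoma therapy during induction with no later scan keep their last response in the primary ORR; the rule can only raise the ORR or leave it unchanged

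*Combined protocol and SAP*

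**What the plan says.** The Synopsis defines the primary endpoint as investigator-assessed "Overall response rate (ORR) at the end of induction phase", and section 9.3 places the assessment after cycle 6, using the 2014 Lugano criteria.

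Section 9.3 then gives the substitution rule: "Last available clinical response will be considered for patients who will permanently discontinue both drugs of the experimental combination before the completion" of cycle 6, for any cause. The Synopsis (Statistical considerations) and section 17.1 repeat it. The Synopsis and section 9.3 name one group that is set to non-response: patients with no tumour assessment after starting therapy. Section 17.3 keeps every patient who received at least one dose in the analysis.

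The parts of the plan that bear on how often the rule applies are:

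- **Restaging.** CT and PET are done after cycle 3, within 7 days before day 1 of cycle 4, and again at the end of induction (section 15.3).
- **Unscheduled scans.** CT and PET are also due at early withdrawal and at relapse or progression (section 10.1).
- **Waiver.** Section 15.8 qualifies the withdrawal scan: "FDG-PET scan (mandatory) unless the subject already has had per-protocol scan" within the preceding 4 weeks. The CT carries the same waiver.
- **New therapy.** Any other lymphoma treatment ends all study treatment (section 13.10).
- **PFS.** Progression and death from any cause are events (section 9.4).

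**The concern.** The endpoint is described as a status at about week 24 (6 cycles of 28 days). For some patients the substitution rule replaces it with a status seen at about week 12. That is reasonable for a patient who stops for toxicity and is still in remission on the withdrawal scan. It is not reasonable for a patient who has died, or who needed another lymphoma treatment before the end-of-induction assessment. The same death would be a success in the primary endpoint and a failure in PFS.

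Early loss of patients is foreseeable with this regimen. Section 13.11 reports fatal and/or serious infections in 21% to 48% of idelalisib-treated patients. Section 13.12 says that serious and fatal infections have been most frequent in the first 6 months of idelalisib treatment, which covers induction. The decision rests on a count in 43 patients, so the classification of one or two of them can settle the result.

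**Working it through.** **1. The plan's own figures.** The inputs are in section 17.1: null rate 0.55, alternative 0.75, 15 patients in stage 1 and 28 more in stage 2. The rules are "If there are 9 or fewer responses in these 15 patients, the study will be stopped" and "The null hypothesis will be rejected if 29 or more responses are observed in 43 patients". The exact rejection probability at a true counted response rate p is

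P(reject | p) = Σ over x = 10 to 15 of C(15, x) p^x (1 − p)^(15 − x) × P[Bin(28, p) ≥ 29 − x].

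- At p = 0.55: 4.96% (stated 5%); probability of stopping at stage 1, 73.9%.
- At p = 0.75: 80.5% (stated 80%).

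A search for the Simon optimal design at these settings returns the same boundaries, 9/15 and 28/43. The design reproduces.

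**2. Who is carried forward.** For patients who stop both drugs before completing cycle 6, sections 9.3, 10.1, 13.10, 15.3 and 15.8 together give:

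| Situation after a PR or CR at cycle 3 | Later scan due? | Counted as |
|---|---|---|
| Dies in cycles 4–6 with no later scan | None possible | Responder |
| Starts new therapy in cycles 4–6, no later scan | Due at withdrawal; may be waived or missed | Responder if no scan |
| Progression documented on a scan | Done | Non-responder (last available is PD) |
| Clinical progression only | Due; may be waived or missed | Responder if no scan, unless the investigator's judgement counts as a response category, which is not defined |
| Stops for toxicity, scan shows PR | Done | Responder |

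**3. Reach of the waiver.** The cycle-3 scan falls 0 to 7 days before day 1 of cycle 4. A 4-week waiver lets it stand for 28 days, which is 21 to 28 days after day 1 of cycle 4 (28 − 7 = 21; 28 − 0 = 28). It therefore excuses a withdrawal scan only until about the end of cycle 4.

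**4. Sensitivity of the decision.** The documents give no rate of death, new therapy or unscanned progression between cycle 3 and the end of induction, so the excess k is an assumption. Suppose the true end-of-induction rate is 55% and carry-forward adds an expected k responses per 43 patients. The counted rate is p = 0.55 + k/43, applied in both stages.

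| k | p | Stops at stage 1 | P(reject) |
|---|---|---|---|
| 0 | 0.5500 | 73.9% | 4.96% |
| 1 | 0.5733 | 67.6% | 8.7% |
| 2 | 0.5965 | 60.8% | 14.3% |
| 3 | 0.6198 | 53.4% | 21.9% |

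One patient moves the final ORR by 1/43 = 2.3 points and the stage 1 rate by 1/15 = 6.7 points.

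**5. Cost of the stricter definition.** If the planned 75% already included such patients, counting them as non-responders lowers the rate at which the trial is powered. Power is 80.5% with no reduction, 72.9% with a 2-point reduction (0.73) and 59.2% with a 5-point reduction (0.70).

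**The case against.** The strongest reply is that the rule has a short reach. It carries the last available response, not the cycle-3 response as such. A living patient who withdraws or progresses is due CT and PET, and that result replaces the cycle-3 one. The waiver covers little more than cycle 4. It may cover less: section 10.1 labels the early-withdrawal assessment EOT, and section 15.4 times EOT at 4 to 6 weeks after the last administration. A cycle-3 scan taken before the last dose would then generally be too old for the waiver. Section 15.8 gives no timing, so this is one reading. The rule also does not cover a death or new therapy after cycle 6 but before the scan, or a patient who continues one drug and misses the scan. The plan does not say how those cases are classified.

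On size, k = 3 means about 3 of 26.65 counted responders (0.55 × 43 + 3), or 11%, failing unscanned within roughly 12 weeks. The plan does not predict that. The 55% null comes from a study that dosed idelalisib until progression or withdrawal (section 7.2), and its rate is not stated to be a week-24 rate. Finally, the rule is prespecified and consistent across three places, the denominator is all treated patients, and death and progression are captured in PFS.

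Most of this stands and sets the limits of the point. It does not answer the core case. A patient who dies cannot have the later scan, and no sentence makes that death, or the start of new therapy, a non-response. There is also no cut-off that bars an assessment made after new therapy from being the last available one.

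**Conclusion.** The point holds in this limited form. As written, a patient in response after cycle 3 who stops both drugs through death or new anti-lymphoma therapy, with no later scan, is an end-of-induction responder. Unscanned clinical progression is treated the same way only if the due scan is missed or waived. Relative to counting these patients as non-responders, the error has one direction: the ORR rises or stays the same.

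A reader might infer that every cycle-3 response is frozen as the end-of-induction result, or that progression in general is scored as response. The documents do not support this: scans are due at withdrawal and progression, and a documented PD is itself the last available response. A reader might also infer that the 5% error rate is breached. That does not follow either, because the number of carried-forward responses is unknown and the null is not stated to be an end-of-induction rate. The figures of 8.7%, 14.3% and 21.9% show how sensitive the decision is to an assumed excess of 1, 2 or 3 responses. They are not estimates of the trial's actual error rate. The point should be settled before the primary analysis; it does not call the design into question.

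**What to change.** In the Synopsis (Statistical considerations) and sections 9.3 and 17.1:

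1. State that death, progression (including clinical progression) or start of new anti-lymphoma therapy before the end-of-induction assessment counts as non-response. This also settles those events when they occur after cycle 6 but before the scan, or in a patient continuing one drug.
2. State that only assessments made before new anti-lymphoma therapy can serve as the last available response.
3. Prespecify a supportive ORR in which every patient without an end-of-induction assessment is a non-responder. This also shows the effect of scans missed for other reasons.
4. Report the number of carried-forward responses, with the reason for stopping.

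The cost is a sentence or two repeated in three places and one extra table. Sample size, boundaries and patient care are unchanged. The ORR may be slightly lower. If the planned 75% included such patients, some power is lost: about 8 percentage points for a 2-point drop in the rate (80.5% to 72.9%), and more for a larger drop.
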